#### 4. Discussion

Patients with EDs have a number of psychotherapeutic options, particularly CBT-E, but nonresponse, partial response and dropout remain challenges for treatment. We proposed that adding treatment components focusing on poor metacognition (the capacity to make sense of mental states and use psychological knowledge to promote emotion regulation; Dimaggio & Lysaker, 2010; Semerari et al., 2003; 2014) and maladaptive interpersonal schemas would offer adjunctive therapeutic options to address problematic eating behaviors. In this pilot RCT we considered these components from MIT as a bolt-on to a commonly used, empirically validated psychological intervention (CBT-E).

We hypothesize that the CBT-F+MIT arm will result as highly tolerable in terms of session attendance and dropouts. We expect possible <10-15% dropouts which would be above the average 17.51% found across evidence-based treatments (Grenon et al., 2019). Low dropout rate is a feature of existing MIT protocols for complex mental health problems such as personality disorders, psychosis, either as a solo treatment (Dimaggio et al., 2017; Gordon-King et al., 2018; Inchausti et al., 2018, 2020; 2022; Popolo et al., 2018; 2019; 2021; Simonsen et al., 2021) or combined with other treatments such as combining metacognition-based interventions with compassion focused practices (Cheli et al., 2022).

The main limitations of this pilot RCT are the small sample, with only 20 patients randomized to either of the 2 arms, possibly limiting scope to observe treatment specific effects. That said use of mixed effects modelling and confidence interval derived analyses may mitigate this problem. The trial will be an initial test of this new treatment combination. Further studies with larger samples and other ED based presentations will be warranted.

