Intolerance of Emotions has been identified as a potentially transdiagnostic factor, albeit in a subgroup of patient with EDs (Meyer et al., 1998; Steinberg et al., 1990; Stice, 1994; Waller, 2002). These individuals present with difficulties in effectively coping with emotional states, both negative and positive. Emotion regulation is often arrived at via dysfunctional strategies such as self-harm or alcohol and substance misuse (Claes et al., 2001; Holderness et al., 1994; Paul et al., 2002).

Finally, with regard to Interpersonal Difficulties studies have shown that a dysfunctional family environment is associated with a higher risk of continuing with restrictive eating behaviors, particularly in younger patients, intensifying a need for a perceived sense of "control". Examples are dysfunctional food-related activities such as controlling food intake and calories, as a response to a perceived hostile interpersonal environment (Fairburn et al., 1999). Bulimia nervosa has also been associated with interpersonal sensitivity in social interactions, further associated with self-criticism and lowered mood (Steiger et al., 1999). In general, poor interpersonal functioning has also been

identified as a predictor of poorer treatment response (Agras et al., 2000a; Steiger, Leung, & Thibaudeau, 1993).

Given the importance of transdiagnostic elements, an enhanced form of CBT was developed, adding a therapeutic focus on these maintenance factors (CBT-E; Fairburn, 2008) to CBT-focused (CBT-f, Fairburn et al, 2003) which originally included psycho-education, nutritional re-education and overall clinical management for ED.

CBT-E has demonstrated acceptability and effectiveness for all forms of EDs (Cooper & Fairburn, 2011; Fairborn et al., 2003) including anorexia nervosa (Dalle Grave et al., 2013a; Dalle Grave et al., 2013b; Dalle Grave et al., 2014; Fairburn et al., 2013; Zipfel et al. 2014), bulimia nervosa (Poulsen et al., 2014; Wonderlich et al., 2014), and intransdiagnostic samples (Fairburn et al. 2009) both in adults (Fairburn et al, 2009; Fairburn et al, 2013) and in younger patients (Dalle Grave et al, 2013). In a direct comparison with interpersonal psychotherapy for adults (IPT), CBT-E was found to be more effective (Fairburn et al, 2015) in patients with EDs.

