### Method/Design

### 2.1 Aims and hypotheses

The study is a pilot randomized controlled trial that aims to evaluate the feasibility and effectiveness of weekly MIT in addiction to CBT-F in a group of adults diagnosed with ED. Specifically, we will investigate in a sample of non-underweight adults presenting with ED whether once compared to CBT-E, a treatment combining MIT and CBT-F is a) feasible, b) well-tolerated and c) potentially effective on eating disorders symptoms and other outcomes. The study is defined according to the Standard Protocol Items: Recommendations for Interventional Trials (SPIRIT) statement and guidelines (Chan et al., 2013).

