### 2.3 Methods

Patients will be assessed and treated by the *Centro di Trattamento Integrato - Disturbi Alimentari e Obesità* (*CTI-Disturbi Alimentari e Obesità*). Two therapists will be involved in the trial: one CBT-trained, the other trained in both CBT-F and MIT. Both therapists will be supervised throughout the trial. The CBT-E arm will be supervised by a certified Associazione Disturbi Alimentari (ADA) supervisor, the MIT/CBT-F arm will be supervised by one of the developers of MIT, also a trainer of the Società Italiana di Terapia Comportamentale e Cognitiva (SITCC). A research assistant will manage the psychometric test administration and will liaise regularly with the clinical team.

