#### 2.4 Participants

Twenty consecutive participants will be recruited at the CTI Disturbi Alimentari e Obesità. All participants will be aged 18 years or over and treatment-naive. They will be screened for a main diagnosis of ED in the past 6 months. Inclusion and exclusion criteria are reported in Table 1.

Inclusion Criteria	Exclusion Criteria
Aged >18 years	Acute psychotic episode, psychotic symptoms, Bipolar I disorder; antisocial personality disorder
ED diagnosed in the past 6 months	Suicidal ideation
Seeking treatment for eating disorder	Substance abuse
Able to provide written, informed consent	Previous psychological intervention for other eating disorders
BMI > 18.5	Currently involved in other ongoing treatment

Table1 Inclusion and Exclusion Criteria

All participants meeting inclusion criteria will be informed about the trial and will decide whether to take part. A regular ED-focused treatment will be offered to all participants excluded from the trial or who decline participating. All participants will give written informed consent before participation.

Drop-out rates from each arm will be reported for patients withdrawing during treatment and those lost to follow-up. Treatment is delivered in a private center therefore participants are paying for their care, however there is no financial incentive to participate in the trial. The study protocol is written in accordance with the European Union Standards of good clinical practice and in accordance with the Declaration of Helsinki. The protocol has been approved by the Ethics Committee of the Department of Dynamic and Clinical Psychology of "La Sapienza" University (Rome) Prot. n. 0000781, 05/13/2022 - [UOR: SI000092 - Classif. VII/15]

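### Tolerability, one of three aims, is given content only as attendance and dropout, so harms in patients who stay and reasons for leaving need not enter the conclusion

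*Combined protocol and SAP*

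**What the plan says.** Section 2.1 asks whether the combined treatment, compared with CBT-E, is "a) feasible, b) well-tolerated and c) potentially effective on eating disorders symptoms and other outcomes". The outcome list in Section 2.2 covers eating disorder and comorbid symptoms, anxiety, depression, global symptoms and emotional difficulties. Tolerability is not in that list.

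The wording that turns tolerability into something measurable is in Section 4: "We hypothesize that the CBT-F+MIT arm will result as highly tolerable in terms of session attendance and dropouts". The same section gives an expectation: "We expect possible <10-15% dropouts which would be above the average 17.51% found across evidence-based treatments". (The word for higher is presumably a slip for lower; nothing here depends on it.)

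Section 2.4 commits to one of the two indicators: "Drop-out rates from each arm will be reported for patients withdrawing during treatment and those lost to follow-up". It also notes that "Treatment is delivered in a private center therefore participants are paying for their care", and Table 1 lists "Suicidal ideation" as an exclusion. The Introduction says of a subgroup of these patients: "Emotion regulation is often arrived at via dysfunctional strategies such as self-harm or alcohol and substance misuse".

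Section 3 describes mainly descriptive analyses with exploratory models. It uses the number of sessions received as a possible moderator and names no tolerability analysis.

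**The concern.** Attendance and dropout describe whether patients keep coming. They do not describe what happens to those who do. The plan itself points to self-harm as relevant in part of this population and screens out suicidal ideation at entry, yet after entry neither is named as an outcome. A patient who attends all 20 sessions and harms herself during treatment would count as a tolerability success on both indicators.

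Dropout is split by timing only. Because patients pay for treatment, some may stop for cost, others because they feel worse, others because they feel better. These have different meanings for tolerability and would be counted alike.

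The pilot is presented as a first test ahead of larger studies, so its tolerability statement will be carried forward. Events and reasons that nobody asked about at the time cannot be reliably recovered afterwards.

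**Working it through.** The plan has no calculation on this point to reproduce. The first step compares sections; the others are simple arithmetic.

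**1. Where could a harm or a reason for leaving enter the tolerability conclusion?**

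- Section 2.1: aim named, no measure attached.
- Section 2.2: outcome hierarchy without tolerability.
- Section 2.4: dropout rates per arm, during treatment or lost to follow-up; no reasons.
- Section 2.5: symptom scales, a diagnostic interview and an alliance scale; no adverse-event instrument.
- Section 2.7.2: a review session two weeks after therapy in both arms; no rule for recording or reporting what is found.
- Section 2.7.3: recordings used for adherence and for the process of change.
- Section 3: treatment effects on the scales, mediators, a moderator, and sub-samples with good and poor outcomes used to study mechanisms.
- Section 4: attendance and dropout.

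No listed item carries an individual harm, or a reason for leaving, into aim (b).

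**2. What does dropout alone tell at this size?** Input: 10 per arm (Section 2.2). Exact (Clopper-Pearson) 95% intervals, with limits from the beta distribution:

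- 0/10: 0 to 1 − 0.025^(1/10) = 30.8%
- 1/10: 0.3% to 44.5%
- 2/10: 2.5% to 55.6%

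An observed 0, 1 or 2 dropouts is compatible with the 17.51% average that the plan cites. None of these results says anything about the 8 to 10 patients who stay.

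**3. What would added harm counts tell?** The chance of seeing at least one affected patient among 10 is 1 − (1 − p)^10. The documents give no rate, so p is an assumption:

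- p = 5%: 1 − 0.95^10 = 40%
- p = 10%: 1 − 0.90^10 = 65%
- p = 20%: 1 − 0.80^10 = 89%

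The counts would often show a harm if it is not rare. A zero would not exclude one (upper limit 30.8%, as above).

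**4. If a deterioration count on the EDE-Q6 is added, how many patients would be flagged by noise?** Assume no true change and independent normal errors of equal size at every assessment, with one shared baseline.

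- Any score worse than baseline, one time point: 10 × 0.5 = 5 of 10.
- Worse by more than 1.96 standard errors of the difference, one time point: 10 × 0.025 = 0.25 of 10.
- The same threshold met at any of k assessments: 10 × ∫ φ(b)[1 − Φ(b + 1.96√2)^k] db, where b is the baseline error in units of its standard deviation.

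Section 2.5 gives seven post-baseline assessments: after 10 sessions, end of treatment, and 3, 6, 12, 18 and 24 months. The formula gives about 0.45 of 10 for the two up to end of treatment, 0.91 for the five follow-ups and 1.15 for all seven. A count of patients who ever worsened would thus produce about one false deterioration per arm, so one time point must be named.

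**The case against.** The plan is not silent. It has a narrow working definition, placed in the Discussion, and Section 2.4 commits to reporting one of its components. Moving that wording to Methods would be editorial, and widening it to self-harm and admissions is partly a choice of what tolerability means. There are also partial sources of information on harm: repeated symptom scales in both arms, poor-outcome sub-samples, the review session after therapy, and a research assistant in regular contact with the clinical team. All of this stands. It means that average worsening could show and that a serious event might well become known. It does not supply a count by arm, and none of it is tied to aim (b).

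Four stronger readings are tempting and not supported:

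- That the trial will not ask about suicidality or self-harm at all. The depression and general symptom scales are repeated, but their items are not reproduced, so this cannot be settled either way. What can be said is that no such item is designated as a tolerability outcome.
- That no safety procedure exists. Some pages and a figure are not available, so the point holds for the available text only.
- That the plan will declare success if dropout falls under 10% or 15%. That figure is stated as an expectation, not as a criterion.
- That having a different therapist in each arm is part of this defect. It is a separate design matter, which affects attendance and dropout equally and which the change proposed here would not remove.

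Finally, both arms have 20 weekly sessions at the same centre and no cost difference is documented. Unrecorded reasons therefore mainly blur what the dropout rate means, more than they bias the comparison of arms.

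**Conclusion.** The concern holds in limited form. A stated aim rests on two indicators that cannot register harm in patients who stay, and one of them does not distinguish worsening from other reasons for leaving. Followed as written, the plan permits a favourable tolerability statement with neither counted.

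The size is that of a gap in measurement, not of a bias that can be estimated. At 10 per arm even a perfect record of no events leaves an upper 95% limit of 31%, so the remedy improves what can be described and does not make the pilot a safety study. The change is worth making because it is cheap and the information is lost if not asked for at the time. It does not put the efficacy analyses in question.

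This rests on the available text being complete for Methods and Section 3. The noise figures in step 4 rest on the error model stated there.

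**What to change.** In Sections 2.1 and 3, define tolerability as:

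1. sessions attended;
2. dropout with its reason (for example worsening or distress, burden, cost, improvement, other);
3. the number of patients per arm with suicidality or self-harm, or with emergency care or admission.

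The research assistant asks about item 3 in the same words in both arms at each existing assessment, and asks the reason when a patient stops. Report the counts descriptively with exact 95% intervals, separately for the treatment period and follow-up.

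If a deterioration count is wanted, define it on the EDE-Q6 at end of treatment only, with the threshold (for example 1.96 standard errors of the difference) and the reliability value behind it fixed before data are seen.

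Cost: protocol wording, a few questions at assessments already planned, one question at dropout and a short log; no new visit and no added patients. Downsides: the counts depend on disclosure and on reaching patients who leave, and at this size they cannot establish safety.
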